#### Service evaluation procedures flow chart

# 8. PRACTICE IDENTIFICATION

# 8.1. Participating practices

We will work with approximately 60 GP practices (approximately 15 practices from each participating CCG) from areas that are taking part in the Omron Hypertension Plus first phase roll out and use a compatible Electronic Health Record (EHR) system. The precise number of practices will depend on the final number of practices in the first wave using an EHR system.

All participating practices must satisfy the following criteria:

- Practice is using (or planning to use) the Hypertension Plus telemonitoring system
- Utilises compatible EHR system
- Data available for the previous 2 years from practice recruitment are available

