# 8.3. Study Patient Records

TM101-A

Protocol Template for a Research Study\_version 15.0 CONFIDENTIAL
© Copyright: The University of Oxford and Oxford University Hospitals NHS Foundation Trust 2019 Page 13 of
28

Outcome data for adult patients (>18 y) and on the hypertension register will be extracted from the EHR at each participating practice by electronic search and provided in an anonymised form to the analysis team.

Active users of the intervention will be defined as:

- Adults aged 18 years or above.
- Diagnosed with hypertension on practice hypertension registers whose baseline blood pressure is above 140/90mmHg on last recorded reading at baseline
- Registered users of the Hypertension Plus telemonitoring system with coded data in the clinical record identifying them as such

These will be compared to patients not using the system who are:

- Adults aged 18 years or above
- Diagnosed with hypertension on practice hypertension registers whose baseline blood pressure is above 140/90mmHg on last recorded reading at baseline
- With no record of using the Hypertension Plus telemonitoring system coded in the clinical record.

An exploratory analysis will examine people in the two groups above who have a blood pressure  $\leq$ 140/90mmHg at baseline, with the same comparison between users and non users of the system.

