#### Outcomes

Primary outcome: Systolic blood pressure (SBP) in mm Hg. Blood pressure readings will be extracted from the electronic healthcare record and from the Hypertension Plus system. Readings will be identified as having been taken by a healthcare professional in the clinic or by the patient at home. Readings derived from 24-hour ambulatory BP monitoring will be excluded. Values outside the range 70-250 mm Hg will be excluded. Where multiple readings are recorded on a single day, the lowest value will be selected.

Secondary outcomes:

- Diastolic blood pressure (DBP) in mm Hg, extracted from the electronic healthcare record or the Hypertension Plus system in the same manner as SBP readings. Values outside the range 40-150 mm Hg will be excluded.
- Blood pressure control (binary variable) defined using SBP and DBP readings. Controlled BP will be defined as SBP <140 mm Hg and DBP <90 mm Hg for clinic readings or SBP <135 mm Hg and DBP<85 mm Hg for home readings. Uncontrolled BP will be defined as the presence of any clinic or home SBP or DBP reading above these thresholds.
- Primary care workload defined as the number of face-to-face and telephone consultations where hypertension or hypertension monitoring was listed as the primary problem. Sensitivity analyses will assess whether the addition of BP readings or antihypertensive treatment records to the definition of workload affects these results

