#### Timeframe of outcome measurement

"Time 0" for exposed patients will be the date on which they start using the Hypertension Plus monitoring system. For unexposed patients "Time 0" will be the median date on which exposed patients in the same general practice started using the Hypertension Plus system. Longitudinal data for all TM101-A

Protocol Template for a Research Study\_version 15.0CONFIDENTIAL© Copyright: The University of Oxford and Oxford University Hospitals NHS Foundation Trust 2019Page 17 of28

outcomes (BP measurements, consultation dates etc.) will be extracted from patient's electronic health record from the 12 months before and after "Time 0" for all patients.

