Model assumptions will be checked by producing histograms of residuals and scatter plots of residuals against fitted values. If there is evidence of violation of assumptions, models will be refitted to log-transformations of SBP and DBP and assumptions re-checked.

• Secondary BP control outcome:

For the secondary outcome of BP control, a multilevel logistic regression model will be fitted to the BP control data, using the same steps as described above for the BP outcomes above.

• Primary care workload:

The number of primary care consultations occurring before and after "Time 0" will be totalled separately and modelled using a negative binomial model, including an offset term for person-time of follow-up (to account for potential loss-to-follow-up). This model will include an indicator for time before/ after "Time 0", an indicator for the exposure variable, and an interaction between these variables. Random effects for the patient and practice will also be included and robust standard errors will be estimated similar to other models.

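### Workload is compared over a fixed year before Time 0, with no minimum time since diagnosis and no diagnosis date extracted, so recent diagnoses can distort the before/after contrasts

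*Protocol*

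**What the plan says.** - **Outcome** (Protocol 11.2, Outcomes): workload is "the number of face-to-face and telephone consultations where hypertension or hypertension monitoring was listed as the primary problem". The planned variation concerns only what is counted: "Sensitivity analyses will assess whether the addition of BP readings or antihypertensive treatment records to the definition of workload affects these results".
- **Window** (Protocol 11.2, Timeframe of outcome measurement): data "will be extracted from patient's electronic health record from the 12 months before and after" Time 0, for all patients. A user's Time 0 is their own start date. A non-user's "will be the median date on which exposed patients in the same general practice started using the Hypertension Plus system".
- **Eligibility** (Protocol 8.3): users and non-users must both be "Diagnosed with hypertension on practice hypertension registers whose baseline blood pressure is above 140/90mmHg on last recorded reading at baseline". No duration is attached. The two-year rule in 8.1, "Data available for the previous 2 years from practice recruitment are available", is a condition on the practice, not on the patient.
- **Model** (Protocol 11.2, Statistical modelling): before and after counts enter a negative binomial model with a period indicator, an exposure indicator and their interaction, "including an offset term for person-time of follow-up (to account for potential loss-to-follow-up").
- **Data items**: date or duration of hypertension diagnosis is absent from the extraction list (9.6), the covariates and subgroups (11.2) and the bias table (12.3).
- **Comparison**: the synopsis and the outcome table set the workload question as the first year of use against the year before. The costs in 12.5 use the same two 12-month windows.

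**The concern.** The before-year is treated as the same kind of period as the after-year for everyone. For a patient diagnosed within it, it is not. Before diagnosis, a consultation is less likely to carry hypertension as its primary problem. Around diagnosis there is likely to be a cluster of visits. Blood pressure readings from before diagnosis are untreated. The after-year has none of these features, so moving from undiagnosed to diagnosed and treated shows up as a before/after change whether or not the system does anything.

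A plain before/after comparison carries this directly. Difference-in-differences removes it only if the share and pattern of recent diagnoses match in the two groups, and nothing in the design secures that. Patients choose the system with their clinician (9.4), section 12.3 accepts that the groups may differ systematically at baseline, and Time 0 is set differently in each group. At stake are the workload answer, the cost analysis built on the same windows, and to a smaller extent the primary systolic pressure estimate.

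**Working it through.** The protocol gives no consultation rate, effect size or power for workload, so there is no workload figure to reproduce. What follows illustrates the mechanism with no true effect of the system.

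**Inputs from the protocol:** 12 months before and after Time 0; a period-by-exposure interaction as the estimate; planning effects for systolic pressure of -3 and -1 mm Hg (11.2, sample size text).

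**Assumptions (not in the protocol):** a share q of patients is diagnosed during the before-year, with q from 5% to 30%; diagnosis dates are spread evenly, so on average half of that year precedes diagnosis; before diagnosis the rate of hypertension-coded consultations is a fraction r of the later rate; diagnosis adds b times the annual rate in extra visits; starting treatment lowers systolic pressure by 10 mm Hg.

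**Workload.** Before-year rate relative to the after-year:

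B(q) = 1 - 0.5 × q × (1 - r) + q × b

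Spurious before/after ratio = 1 / B(q). Spurious ratio of rate ratios = B(q non-users) / B(q users).

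*Before/after only, r = 0, b = 0:*
- q = 10%: 1 / 0.95 = 1.053
- q = 20%: 1 / 0.90 = 1.111

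*Difference-in-differences, r = 0, b = 0:*

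| Users v non-users recently diagnosed | Calculation | Ratio |
|---|---|---|
| equal shares | | 1.00 |
| 10% v 5% | 0.975 / 0.95 | 1.026 |
| 20% v 5% | 0.975 / 0.90 | 1.083 |
| 30% v 5% | 0.975 / 0.85 | 1.147 |
| 5% v 20% | 0.90 / 0.975 | 0.923 |

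*20% v 5%, other assumptions varied:*

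| r | b | Calculation | Ratio |
|---|---|---|---|
| 0.5 | 0 | 0.9875 / 0.95 | 1.039 |
| 0 | 0.5 | 1.00 / 1.00 | 1.00 |
| 0 | 1 | 1.025 / 1.10 | 0.932 |
| 0 | 2 | 1.075 / 1.30 | 0.827 |

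The sign therefore depends on how many visits diagnosis generates, and on which group has more recent diagnoses.

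**Systolic pressure.** With readings evenly spread and treatment starting at diagnosis, half of a recently diagnosed patient's before-year is untreated, so that patient's before/after contrast is 0.5 × 10 = 5 mm Hg. Bias in the difference-in-differences = -(q users - q non-users) × 5:
- 10% v 5%: -0.05 × 5 = -0.25 mm Hg
- 20% v 5%: -0.15 × 5 = -0.75 mm Hg
- 30% v 5%: -0.25 × 5 = -1.25 mm Hg

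The middle value is a quarter of the -3 mm Hg planning effect and three quarters of the -1 mm Hg one.

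**Does another part of the plan absorb this?** The offset is explained by loss to follow-up, and nothing says that before-period person-time starts at diagnosis. Covariates are fixed at Time 0 and enter as main effects. They shift the level of the outcome but do not absorb a before/after change particular to new diagnoses. The workload sensitivity analyses leave the window and the population as they are.

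**The case against.** The strongest reply is that the planned estimate is a difference-in-differences, which cancels the artefact if recent diagnosis is equally common in both groups. This stands as a limit. A reader might infer that users must be more recently diagnosed, because people take up such a system when treatment begins. The protocol does not say so: section 9.4 says only that patients choose with their health care professionals. The imbalance is possible, not shown.

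A reader might also conclude that workload will be biased upwards, or that no consultation can be coded before diagnosis. Neither is supported. Diagnostic visits can cancel or reverse the ratio, and the outcome includes hypertension monitoring, which may cover work-up.

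Taking the whole before-year as untreated would double the systolic pressure figures, to -1.5 mm Hg at 20% v 5%. That does not fit diagnoses spread over the year, with treatment from diagnosis. For users, moreover, treatment adjusted through the system may be part of its effect.

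Nor is the problem wholly invisible in the planned data. Antihypertensive drug and dose, consultation timing (9.6) and 12 months of prior resource use (12.5) would reveal some new starters. They are a proxy for the diagnosis date, not a substitute.

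Repeat extraction at 6 and 12 months might suggest that non-users diagnosed after Time 0 will enter. Section 8.3 ties eligibility to the last reading at baseline, so this is only a possibility.

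Finally, the start of person-time and an extra sensitivity run could be left to an analysis plan. That is fair for the modelling detail, but not for the data item. Section 13.3 has coded data anonymised at source and pulled by automatic search, so a date left off the list cannot be assumed recoverable later.

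**Conclusion.** The point holds as a limited one. The protocol compares a fixed before-year with an after-year, sets no minimum time since diagnosis, and does not collect the date needed to check the consequence. The before/after contrast is exposed wherever recent diagnoses occur, unless the opposing parts happen to cancel. The difference-in-differences estimate is exposed only if recency of diagnosis differs between users and non-users.

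Under an assumed 20% v 5%, the workload ratio of rate ratios with no true effect lies between about 1.08 and 0.83, with the sign undetermined. The systolic pressure bias is about -0.75 mm Hg (-0.25 to -1.25 for 10% to 30% v 5%). These figures rest on assumed shares, an assumed 10 mm Hg treatment fall and evenly spread diagnoses. The protocol fixes none of them, so confidence in the size is low. The change is worth making because it is cheap and deals with the artefact whichever way it runs.

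**What to change.** 1. Add the date of first hypertension code to the extraction list in section 9.6, before the searches are written.
2. State in section 8.3 that this date must precede Time 0 in both groups.
3. Pre-specify a repeat of the workload, cost and systolic pressure analyses restricted to patients diagnosed at least 12 months before Time 0. In the illustration this returns the spurious ratio to 1.00 and takes the diagnostic visits out of the before-year.

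Starting each patient's before-period and offset at diagnosis should not be the main remedy. It corrects the coverage but packs the diagnostic visits into a short denominator, which raises the before-rate and could make the system appear to reduce workload.

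Cost: one more coded date in an electronic search that already selects on a hypertension code, one extra analysis run, and somewhat fewer patients in that run.

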# 3. SYNOPSIS

Study Title	A Service evaluation of the Hypertension-Plus Implementation – implementing a hypertension self-monitoring/management service in primary care				
Internal ref. no. / short title	The SHIP study				
Study registration	tbc				
Sponsor	University of Oxford Joint Research Office [name]				
Funder	NIHR ARC Oxford and Thames Valley [name] [name] [name] [contact] Email: arc. [contact]				
Study Design	Observational Service	e Evaluation			
Study Sites	GP practices				
Study Participants	Adult patients (>18y) with hypertension				
Sample Size	Anonymised records	from approximately 60 practices			
Planned Study Period	From January 2022 fo following recruitment	er around 12 months with follow-up t.	o for 12 months		
	Research Questions	Outcome Measures	Timepoint(s)		
Primary	Does Hypertension Plus lead to lower systolic blood pressure?Systolic blood pressure of system us compared to before and o patients		Over the first year of system use compared to year before and control patients		
Secondary	Will people with hypertension use the HypertensionProportion of hypertension register signing up for Hypertension Plus in first 6 months of implementation in each practice.Over the first ye of system use				
	Does Hypertension Plus lead to lower diastolic blood pressure?Diastolic blood pressureOver the first year of system use compared to year before				

	Does Hypertension Plus lead to better control of blood pressure?	Proportion controlled below target	Over the first year of system use compared to year before
	Does Hypertension Plus reduce practice workload?	Consultation rate recorded in clinic record before and after use of Hypertension Plus system	Over the first year of system use compared to year before
Intervention	Hypertension Plus system		
Comparator	We will use both interrupted case series (before/after) and difference of differences approaches meaning that the comparator is usual care without the use of Hypertension Plus. Practices that implement the system later will be used to as a further level of comparator.		

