#### TM101-A

Protocol Template for a Research Study\_version 15.0CONFIDENTIAL© Copyright: The University of Oxford and Oxford University Hospitals NHS Foundation Trust 2019Page 15 of28

- Index of Multiple Deprivation
- Body mass index (kg/m^2)
- Total cholesterol (mmol/L)
- Systolic and diastolic blood pressure (clinic or home readings)
- Ambulatory blood pressure
- SNOMED codes for home blood pressure measurement (in order to identify system users)
- Past medical history:
  - Diagnosis of diabetes (Type 1 or 2)
  - Previous myocardial infarction or stroke
  - Diagnosis of chronic kidney disease
  - o Estimated glomerular filtration rate (eGFR, ml/min/1.73 m^2)
- Medication use
  - Statin treatment (drug type and dose)
  - o Antihypertensive medication use (drug type and dose, defined daily dose)
  - o Other current cardiovascular medication
- Electronic Frailty Index and/or characteristics making up the electronic frailty index 
- Health Economic Resource use including consultation rate, timing, personnel undertaking, referrals and admissions.

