# TM101-A

Protocol Template for a Research Study\_version 15.0

© Copyright: The University of Oxford and Oxford University Hospitals NHS Foundation Trust 2019 Page 21 of 28

		intervention/control in the analysis b) BP control rather than BP level in analyses
(3) High variability in the frequency of readings	Home readings can be several times per day or week whereas clinic readings tending to be 1-4x per year. Furthermore, attendance at clinic may be for some other reason meaning those who attend or not are different systematically	
 
a) Primary analysis utilises all available data
 
b) Consider sensitivity analysis using standardisation of readings over time. This means that we take bp values at fixed time points more specifically at 6 and 12 months with value closest to that time point being the one used for the analysis.
 

(4) Contamination of readings	Home readings can be coded as clinic readings. The automated importing of Hypertension Plus readings into the clinical record should avoid this but it is possible that home readings in the comparator group may also be contaminated as may be readings prior to the implementation period.	
 
a) This may be a problem in both groups
 
b) Hypertension Plus readings will be labelled as such
 

(5) Regression to the mean	People chosen on the basis of raised baseline readings are more likely to have subsequently controlled BP	Both intervention and comparison groups will be chosen using same attributes Consideration of need for matching.
(6) Measurement error	Both operator, system and monitor errors are possible	Operator errors may be more likely by patients but evidence of operator bias is more likely for clinicians. Most of these errors will be similar in both groups
(7) End digit preference	People tend to be more likely to record readings ending in zero	
 
a. We will investigate prevalence in both intervention and comparator groups
 
b. Adjusting for the control/intervention group in a mixed model should be
 

		able to take into account for potential differences in the magnitude of digit preference
(8) Withdrawal bias	Patients may not use the Hypertension Plus system consistently.	We will use intention to treat approach so individuals with any Hypertension Plus activity recorded will be assigned to intervention.

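### The workload outcome counts only hypertension-coded consultations, which is narrower than the question on practice workload and sensitive to coding; an all-reason count should be reported beside it (minor)

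*Protocol*

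**What the plan says.** The workload outcome is described in several places of the protocol.

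- **Section 3 (Synopsis) and the objectives table:** the question is whether the system lowers practice workload, and the measure is "Consultation rate recorded in clinic record before and after use of Hypertension Plus system". Neither reason nor mode of contact is limited.
- **Section 11.2, Outcomes:** workload is defined as the "number of face-to-face and telephone consultations where hypertension or hypertension monitoring was listed as the primary problem". The next sentence adds: "Sensitivity analyses will assess whether the addition of BP readings or antihypertensive treatment records to the definition of workload affects these results".
- **Section 11.2, Statistical modelling, under the workload heading:** "The number of primary care consultations occurring before and after" Time 0 is modelled with a negative binomial model that has a period indicator, an exposure indicator, their interaction, a person-time offset, and random effects for patient and practice. The restriction by reason is not repeated.
- **Section 9.6 (Data Extraction):** the item is "Health Economic Resource use including consultation rate, timing, personnel undertaking, referrals and admissions". Problem code and mode of contact are not named.

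Two other statements bear on coding. Section 7.1 says that the professional dashboard both reads from and writes to the practice clinical system. Section 9.5.1 says that app data enter the clinical record automatically through SNOMED codes.

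**The concern.** A practice's workload from its hypertensive patients is all the contacts it has with them. The governing outcome counts only contacts filed under hypertension. A change in that count can mean that contacts were saved or added, or that the same contacts were filed differently.

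The second possibility matters here because the intervention itself touches the record. Once a patient is on the system, blood pressure work previously done within another visit could become a separate hypertension contact. A former hypertension review could equally be absorbed into a visit coded otherwise. Such a shift would occur in users after Time 0, and that is the contrast that the exposure-by-period interaction estimates.

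At stake is the reading of one secondary result: whether a fall or rise in hypertension-coded contacts can be reported as a change in practice workload.

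**Working it through.** The protocol gives no consultation rate, effect size, dispersion or power for workload, so it has no figure to reproduce. The simulated sample size in Section 11.2 concerns systolic blood pressure only. The check is therefore a reading of the text, followed by illustrative arithmetic on assumed inputs.

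**1. Which definition governs.** Only the Outcomes text of Section 11.2 defines workload. The modelling text reuses the outcome's name in the same section, and the two tables give short labels. No part of the protocol says that consultations for all reasons will be counted. The restricted count is the outcome.

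**2. What the model removes.** Stable differences in coding habit between users and non-users cancel in the difference-in-differences, and stable practice or patient differences are absorbed by the random effects. A coding change common to both groups also cancels. The offset corrects for person-time only. A coding change confined to users after Time 0 is not removed.

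**3. What the planned sensitivity analyses add.** Adding blood pressure readings would pick up work done at visits coded otherwise. It would also count app readings that reach the record automatically, so the count can rise in users without any staff contact. Adding antihypertensive treatment records can raise the count because the system is a medication titration platform (Section 7.1). Neither analysis counts all consultations, so neither separates fewer contacts from recoded contacts.

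**4. Illustration: dilution.** Let s be the share of consultations that are hypertension-coded and RR the rate ratio on them, with other consultations unchanged. The all-reason rate ratio is 1 − s(1 − RR). With RR = 0.80:

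| s (assumed) | Calculation | All-reason ratio |
|---|---|---|
| 10% | 1 − 0.10 × 0.20 | 0.98 |
| 20% | 1 − 0.20 × 0.20 | 0.96 |
| 30% | 1 − 0.30 × 0.20 | 0.94 |
| 50% | 1 − 0.50 × 0.20 | 0.90 |

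This shows only that the two counts answer different questions. It does not show that the restricted one is wrong.

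**5. Illustration: coding shift.** Suppose true hypertension contacts do not change, non-users' coding is stable, and the share of those contacts coded as primary problem in users moves from 60% (assumed). The spurious ratio is the share after divided by the share before:

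- 60% to 50%: 0.50 / 0.60 = 0.83
- 60% to 70%: 0.70 / 0.60 = 1.17

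If only the coding changes, the all-reason ratio stays at 1.00 in both cases.

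**The case against.** The strongest reply is that hypertension-specific contacts are a legitimate measure for a hypertension service. They are more specific than a total dominated by unrelated illness, and they match the health economic outcome in Section 12.5, which is the cost of hypertension care. The protocol also anticipates narrow coding through its own sensitivity analyses. All of this stands, and it is why the restricted count should remain the outcome. The sensitivity analyses are nevertheless an incomplete check, for the reasons in step 3 of the working.

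A reader might infer that the protocol holds two competing definitions and that either could be reported as the answer. The documents do not support this. One text defines the outcome and the others are shorter labels; the blood pressure control outcome is shortened in the same way, without its thresholds. Section 12.4 would also require an unplanned all-reason count to be labelled post hoc.

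A reader might also infer that the extraction list cannot support the restricted count. That goes too far. The list is introduced as inclusive, and Section 11.2 (Timeframe of outcome measurement) provides for extracting longitudinal data for all outcomes.

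The bias table in Section 12.3 does note that "attendance at clinic may be for some other reason", but that row concerns how often readings are taken. It supports the coding mechanism only indirectly. The automatic entries described in Sections 7.1 and 9.5.1 make a shift in consultation coding plausible; they do not show that it occurs.

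**Conclusion.** The point holds as a minor one. The defined workload outcome is narrower than the question it is meant to answer, and a coding change in users after Time 0 would pass straight into its effect estimate. The planned sensitivity analyses address this only in part.

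The size is unknown. The ratios of 0.83 and 1.17 rest on an assumed ten-point move from a 60% coded share, and the 0.98 to 0.90 range rests on assumed shares of 10% to 50% with a ratio of 0.80. None of these inputs is in the protocol, which documents neither the direction nor the size of any shift. The conclusion that the restricted count alone cannot separate saved contacts from recoded ones does not depend on these figures.

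Only one secondary outcome is affected. The primary outcome and the sample size are untouched.

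**What to change.** Keep the hypertension-coded count as the secondary outcome. Prespecify consultations for any reason, in the same patients and with the same negative binomial difference-in-differences model, as a sensitivity analysis reported beside it. Say that a change in hypertension-coded contacts will be interpreted as a change in practice workload only in light of the all-reason result. No formal conclusion rule is needed: the total also reflects unrelated illness, and step 4 of the working shows that a real effect would be small on that scale.

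Two clarifications go with this:

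- Align the wording in the synopsis, the objectives table and the model text with the definition in Section 11.2 (Outcomes).
- Name the primary-problem code and the consultation mode in Section 9.6.

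The cost is some wording, two named fields and one more model on consultation data already planned for extraction. The all-reason count is noisier and may make the workload claim less favourable. It is best settled before data extraction, so that the fields are secured and the analysis is not post hoc.
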